8.3.3. Clinical Laboratory Tests

Blood samples for the safety laboratory tests listed in Table 3 will be collected according to the Schedule of Events (Section 4.6).

Table 3: Safety Laboratory Tests

Hematology

White blood cells (WBC) Platelets

Red blood cells WBC differential (absolute and %)

HemoglobinNeutrophilsHematocritLymphocytesMean corpuscular volumeMonocytesMean corpuscular hemoglobinEosinophilsMean corpuscular hemoglobin concentrationBasophils

Liver Panel

Total and direct bilirubin

Aspartate transaminase (AST)

Alanine aminotransferase (ALT)

Total protein

Albumin

Gamma-glutamyl transferase (GGT)

Lactate dehydrogenase

Alkaline phosphatase (AP)^a

International normalized ratio (INR)

Serum Chemistry

Sodium

Potassium

Urea

Creatinine

Calcium

Phosphate

Glucose

Creatine kinase^b

Urinalysis

Protein Red blood cells

Bilirubin pH Urobilinogen Nitrites

Ketones Specific gravity

Glucose Microscopy (if clinically indicated or Leukocyte esterase hemoglobin is detected on dipstick)

For the purpose of reactogenicity reporting, hematuria is defined as 3 or more red blood

cells per high powered field

Serology (at Screening only)					
HIV I and II	HDV antibodies				
HCV antibodies					
Drugs of abuse and alcohol screen (at Screening only) ^c					
Amphetamine/ecstasy	Opiates				
Ethanol	Benzodiazepines				
Cannabinoids	Methadone and/or metabolites				
Cocaine	Barbiturates				
Pregnancy test ^d					

Pregnancy test

Beta human chorionic gonadotropin

- a Alkaline phosphatase iso-enzymes (liver-specific and bile duct specific) will be measured if original alkaline phosphatase test result is above the upper limit of normal.
- b Creatine kinase MB or Troponin T will be measured where clinically indicated.
- c Sites may use locally available drugs of abuse panels and alcohol tests. The specific drugs may vary from the outlined list.
- d A serum pregnancy test will be performed in all women of childbearing potential at Screening. Urine pregnancy tests will be performed at other time points.

8.3.4. Height, Weight and BMI

Height and weight will be measured and BMI calculated and recorded at Screening. Weight and BMI will also be recorded at end of the Treatment Period (Day 169 or ET) and at the end of the Follow-up Period (Day 505 or ET).

8.3.5. **Physical Examination**

Physical examinations will be performed by trained medical personnel. A complete physical examination will be performed at Screening and the end of the Treatment Period (Day 169 or ET). Targeted and symptom-driven physical examinations will be performed at all other study visits. Any clinically relevant change in physical examination findings will be recorded as AEs.

8.3.6. **Vital Signs**

Vital signs, including sitting blood pressure, pulse rate (after at least 5 minutes rest), and body temperature, will be recorded at every study visit. Patients will stay in the unit for at least 2 hours following administration of the first and second doses. Vital signs will be assessed before dosing and every 15 minutes post dosing over 2 hours at these two visits. At visits with laboratory assessments, vital signs should be measured before any blood sample collection. Any clinically relevant change in vital signs will be recorded as AEs. Significant changes of vital signs, including the occurrence of tachycardia, bradycardia, hypertension, hypotension and fever will categorized and graded according to the FDA Guidance for Industry: Toxicity Grading Scale for Healthy Adult and Adolescent Volunteers Enrolled in Preventive Vaccine Clinical Trials [United States Food and Drug Administration 2007].

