9.3. Assessment of Adverse Events

9.3.1. Severity

The Investigator should assess the severity of each AE. The AE will be recorded at its highest severity grade.

The severity of all AEs, both serious and non-serious, will be assessed by assigning a grade according to the FDA Guidance on the Toxicity Grading Scale for Preventive Vaccine Clinical Trials [United States Food and Drug Administration 2007]. NCI CTCAE, v 5.0 (http://ctep.cancer.gov/protocolDevelopment/electronic applications/ctc.htm) will be used for AEs not described in this guidance.

When an AE cannot be graded by the aforementioned FDA guidance or CTCAE, the following severity grading may be used:

- Grade 1 (Mild): awareness of sign or symptom, but easily tolerated
- Grade 2 (Moderate): discomfort enough to cause interference with usual activity
- Grade 3 (Severe): incapacitating with inability to work or do usual activity

- Grade 4 (Life-Threatening): refers to an event in which the patient was, in the view of the Investigator, at risk of death at the time of the event. (This category is not to be used for an event that hypothetically might have caused death if it were more severe.)
- Grade 5 (Fatal): death related to AE

An AE that is assessed as severe should not be confused with an SAE. Severity is a category for rating the intensity of an event, and both non-serious AEs and SAEs can be assessed as severe. An event will be defined as serious when it meets one of the criteria described in Section 9.1.7.

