5.3.3.2 Adverse events

AEs will be coded using MedDRA v25.1 or subsequent.

Summary of AEs:

The primary focus of AE reporting will be on Treatment-Emergent Adverse Events (TEAEs). A TEAE is defined as an AE that starts or worsens on or after the date and time of the first administration of the study drug.

All reported AEs (regardless of TEAE or not) will be included in a by-patient AE listing, identifying which is treatment emergent and which it not.

If an AE date/time of onset (occurrence, worsening, or becoming serious) is incomplete, an imputation algorithm will be used to classify the AE as treatment-emergent or not. The algorithm for imputing date/time of onset will be conservative and will classify an AE as treatment-emergent unless there is definitive information to determine it is pre-treatment or post-treatment. Details on classification of AEs with missing or partial-onset dates are provided in Section 5.3.9.

AE summaries will include number (n) and percentage (%) of patients experiencing an AE within each treatment arm and overall if appropriate. The denominator for computation of percentages is the number of patients in the safety population within each treatment arm. The number of events will be included in some summaries as well whenever appropriate.

Unless otherwise specified, when applicable, sorting order will be by decreasing number of patients in PTs within SOCs based on total patients. When more than one PT has same number of patients, the order of presentation will be alphabetical in PTs.

Multiple occurrences of the same event in the same patient will be counted only once for patients counting in the tables within a treatment arm.

Summary of All TEAEs:

The following TEAE summaries will be generated for the safety population:

- An overview of TEAEs. Number (%) of patients will be provided by treatment arm, to include:
 - o TEAEs.
 - o MAEs.
 - o Grade 3 (Severe), Grade 4 (Life-threatening), and Grade 5 (Fatal) TEAEs.
 - Serious TEAEs.
 - Treatment-related AEs (defined as those events other than 'Unrelated/Unlikely related' as assessed by the investigator).
 - TEAEs serious leading to death.
 - TEAEs leading to study drug permanent discontinuation.

22-Apr-2024

- TEAEs leading to clinical management of the AE.
- All TEAEs by primary SOC and PT.
- All TEAEs presented by PT.
- All treatment-related AEs presented by primary SOC and PT.
- All treatment-related AEs Grade 3 or higher, presented by primary SOC and PT.

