- All TEAEs by maximum severity (i.e., Grade 1, Grade 2, Grades 3 to 5), presented by primary SOC and PT.

Separate listings will be provided for TEAEs leading to premature study drug discontinuation/interruption and Study-Drug-Related TEAEs

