5.3.3.11 Vital Signs and Height, weight, and BMI

A summary of vital signs (including systolic and diastolic blood pressure and body temperature (in °C), heart rate and respiratory rate) including change from baseline (where appropriate), presented by descriptive statistics, will be displayed by treatment arm and overall, for each visit day from baseline through Day 169. Particularly, for vital signs measured after first and second doses, the maximum value among all values recorded in the 2 hours post-dosing will be taken as the representative for that day in summaries by visit.

Vital Signs data during the treatment period will be summarized in the current visits: Day 1, 8, 29, 36, 57, 85, 113, 141 and 169. Visits Day 64, Day 92, Day 120 and Day 148 for collection of Vital Signs data during the treatment period were removed in the protocol version for which this SAP version is planned.

For patients following previous versions of the protocol, data recorded on the days of the current visits listed above will be used for analyses. Only if there is no data collected in these visits and these patients have additional values in visits previously collected, those data will be used for analyses following the correspondence: Day 64 to Day 85; Day 92 to Day 113; Day 120 to Day 141; Day 148 to Day 169.

In addition, a summary and change from pre-dose of the values measured in the 2 hours post-dose (at 15 minutes intervals) after the first and second doses will be presented using the maximum value among

all values recorded in the 2 hours post-dosing. Pre-dose will be the latest assessment prior to the dose being summarized.

Height, weight, and BMI and the corresponding change from baseline will be summarized for visits after baseline.

Only available data will be used, and missing data will not be imputed. Change from baseline and predose will be calculated only for patients with non-missing values for both the baseline or pre-dose and the time-point of interest and will be missing otherwise.

Vital Signs (on dosing and no-dosing days) and height, weight and BMI after baseline will be listed.

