5.3.17 Changes to Protocol-planned Analyses

According to the protocol, ECG parameters will be summarized by treatment group and protocol specified collection time point and a summary of change from baseline at each protocol specified time point by treatment group will also be presented. However, ECG parameters have not been collected and they are not available for analyses.

22-Apr-2024

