14.3.4.1.3	Summary of Clinical Laboratory Hematology Results: Shift from baseline vs post-baseline category	Safety Population	Yes (Through D169)	
14.3.4.2.1	Summary of pre-dose Values and Change from baseline for Clinical Laboratory Biochemistry Results	Safety Population	Yes (Through D169)	
14.3.4.2.2	Summary of Abnormalities for Clinical Laboratory Biochemistry Results	Safety Population	Yes (Through D169)	
14.3.4.2.3	Summary of Clinical Laboratory Biochemistry Results: Shift from baseline vs post-baseline category	Safety Population	Yes (Through D169)	
14.3.4.3.1	Summary of pre-dose Values for Continuous Urinalysis Results	Safety Population	Yes	
14.3.4.3.2	Summary of Values for Categorical Urinalysis Results	Safety Population	Yes	

TFL Number	Title	Analysis Set	Included in	TOP LINE
			Final report	TABLES
14.3.4.3.3	Summary of Abnormalities for Clinical Laboratory	Safety Population	Yes	
	Urinalysis Results			
14.3.4.3.4	Summary of Clinical Laboratory Urinalysis Results:	Safety Population	Yes	
	Shift from baseline vs post-baseline category			
14.3.5 Reactoger	-			
14.3.5.1	Incidence of Reactogenicity Events	Safety Population	Yes	
14.3.6 Hepatitis F	Flares			
14.3.6.1	Incidence of Hepatitis Flares	Safety Population	Yes	
14.3.6.2	Summary of patients achieving HBsAg loss by Hepatitis Flares	Safety Population	Yes	
14.3.6.3	Logistic Regression Analysis for HBsAg loss by Hepatitis Flares at Day 169	Safety Population	Yes	
14.3.7 Vital Signs	5		,	I
14.3.7.1	Summary of Values and Change from baseline for Vital Signs: Results by Visit	Safety Population	Yes (Through D169)	
14.3.7.2	Summary of Values and Change from pre-dose for Vital Signs: Results after first and second dose	Safety Population	Yes (Through D169)	
14.3.7.3	Summary of Height, weight, and BMI change from baseline	Safety Population	Yes (Through D169)	
14.3.8 Electrocar	diogram Measurements (12-Lead ECG)			
14.3.8.1	Summary of Evaluation for 12-Lead ECG Results	Safety Population	Yes (Through D169)	
14.3.9 Physical E	xamination		,	
14.3.9.1.1	Complete Physical Examination after Baseline (Day 169/ET)	Safety Population	Yes	
14.3.9.1.2	Targeted and symptom-driven Physical Examination after Baseline	Safety Population	Yes (Through D169)	
Listing Number	Examination and Basonile			
16.2.1 Patient's D	Disposition			

22-Apr-2024

TFL Number	Title	Analysis Set	Included in	TOP LINE
			Final report	TABLES
16.2.1.1	Listing of Patient's Disposition and Status	All Patients in DB	Yes	

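### Pulse and blood-pressure changes that are measured but not reported as AEs get no graded count by arm, and falls after Doses 1 and 2 are hidden by a maximum-only summary

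*Protocol*

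**What the plan says.** Protocol 8.3.6 contains two adjacent rules. The first sends some changes into the adverse-event data: "Any clinically relevant change in vital signs will be recorded as AEs". The second concerns significant changes, "including the occurrence of tachycardia, bradycardia, hypertension, hypotension and fever will categorized and graded according to the FDA Guidance for Industry". The same section asks for readings before dosing and at 15-minute intervals for two hours after Doses 1 and 2.

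SAP 5.3.3.11 plans a summary of vital signs, "including change from baseline (where appropriate), presented by descriptive statistics, will be displayed by treatment arm and overall". For Doses 1 and 2 it takes the highest of the two-hour readings as the value for that day, and uses the same highest value for the change from pre-dose. The index has two vital-sign tables besides the one for height, weight and BMI. Table 14.3.7.1 is titled "Summary of Values and Change from baseline for Vital Signs: Results by Visit", and Table 14.3.7.2 is its counterpart for the first and second doses. Neither the text nor the titles mention a grade.

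Two other planned outputs bear on the point. Protocol 9.3.1 grades adverse events on the same scale: "The severity of all AEs, both serious and non-serious, will be assessed by assigning a grade according to the FDA Guidance". SAP 5.3.3.2 then tabulates "All TEAEs by maximum severity (i.e., Grade 1, Grade 2, Grades 3 to 5), presented by primary SOC and PT". SAP 5.3.3.7 summarises solicited reactions, including fever, by arm, dose number and mild, moderate or severe grade.

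**The concern.** The protocol names five categories of vital-sign change and a scale on which to grade them, and the SAP section on vital signs uses neither. This stands out within the SAP. Laboratory data get counts of abnormal results and shift tables (5.3.3.12), and ECG and physical examination get normal and abnormal categories (5.3.3.9 and 5.3.3.10), but vital signs get no categorical summary.

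Safety is a secondary objective. Acute haemodynamic reactions to an adjuvanted injection, if they occur, are likely to be short and confined to a few patients. The frequent readings after the first two doses can detect them. What is at stake is whether the report can say how many patients in each arm reached each grade, for low values as well as high ones.

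**Working it through.** No sample size, power or rate is involved. The check traces each named category from Protocol 8.3.6 to any planned table that shows it by grade and by arm.

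| Category | Graded table by arm | Condition for entering it |
|---|---|---|
| Fever | 14.3.5.1 (diary), also 14.3.1.6 | Diary temperature, daily for 7 days after each dose; no investigator judgement needed for 14.3.5.1 |
| Tachycardia | 14.3.1.6 | Only if recorded as an AE |
| Bradycardia | 14.3.1.6 | Only if recorded as an AE |
| Hypertension | 14.3.1.6 | Only if recorded as an AE |
| Hypotension | 14.3.1.6 | Only if recorded as an AE |

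**Step 1: the AE route.** Under Protocol 8.3.6 and 9.4, a vital-sign measurement becomes an AE when the investigator considers it clinically relevant or significant. It is then graded under 9.3.1 and counted by arm, since "AE summaries will include number (n) and percentage (%) of patients experiencing an AE within each treatment arm". This is a genuine graded comparison, although Grades 3 to 5 are pooled and the table is not split by dose. A reading that would reach a grade but is not reported as an AE does not enter it.

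**Step 2: the vital-sign tables.** Tables that grade the measurements themselves: 0 of 2 (14.3.7.1 and 14.3.7.2). SAP 5.3 does require median, quartiles, minimum and maximum, so one very high reading can appear as an arm's extreme value. The number of patients in each grade cannot be recovered from these statistics.

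**Step 3: the maximum rule.** Readings every 15 minutes over 2 hours give 120 / 15 = 8 post-dose readings per patient per dose. The summary keeps the highest, which is 1 of 8. The consequence differs by direction:

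- A rise is shown if any one of the 8 readings is high.
- A fall is shown only if the highest of the 8 readings is itself low, that is, if all 8 are low. The change from pre-dose is negative only if all 8 lie below the pre-dose value.

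The minimum reported for an arm is then the lowest of the patients' maxima, not the lowest reading. A drop in pulse or blood pressure that recovers within two hours therefore appears in neither 14.3.7.1 nor 14.3.7.2 for the days of Doses 1 and 2. Unless reported as an AE, it is found only in Listing 16.2.11.1. Other visits are not affected by this rule.

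**The case against.** Section 8.3.6 describes study procedures. Its grading sentence follows the rule on recording AEs and names the scale that 9.3.1 uses for AE severity, so it can be read as telling sites how to grade such events. The protocol's analysis section, 10.4.3, plans only summaries of vital signs by group and time point with change from baseline, and the SAP provides these for the treatment period. The excursions left ungraded are those that investigators did not consider clinically relevant. All remain in the listing, and SAP Section 2 says the product will not be tested further.

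Most of this stands, and it rules out two stronger readings that a reader might infer:

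- *That these reactions are never compared between arms by grade.* This is wrong for fever, which has its own graded summary by arm and dose, and wrong for any of the other four that is recorded as an AE.
- *That a planned analysis was removed without being declared in SAP 5.3.17.* That section reports the ECG change, "However, ECG parameters have not been collected and they are not available for analyses", because 10.4.3 had promised ECG parameter summaries. No graded vital-sign table was promised, so there was no such change to declare.

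Two things remain. If 8.3.6 meant AE grading alone, its sentence would add little to 9.3.1, so the text at least allows the reading that the measurements themselves are to be graded. And nothing in the objection addresses post-dose falls: reporting an arm's minimum does not help when each patient contributes only a maximum.

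**Conclusion.** The point holds in a limited form and is of low severity. One of the five named categories, fever, has a graded summary by arm that does not depend on investigator judgement. The other four have one only through AE reporting. When measured but not so reported, they are not counted by grade in any table, and falls after Doses 1 and 2 that recover within two hours are not visible in any vital-sign table.

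The number of patients affected cannot be derived. The documents do not reproduce the scale's cut-offs and do not say how often readings crossed them. The conclusion assumes that the index of tables is complete and that some readings reaching a grade are not recorded as AEs. The gap limits what the safety tables can show. It does not show that any reaction was missed, nor that the SAP's statement on tolerability is wrong. The point still matters after termination, because the treatment-period vital-sign tables remain marked for the final report.

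**What to change.** Add to SAP 5.3.3.11 and to the index one table, on the Safety population, of the number and percentage of patients by worst post-baseline FDA grade in each of the five categories. Present it by arm, and also by dose for Doses 1 and 2. Derive the grade from every reading: highs for tachycardia, hypertension and fever, and lows for bradycardia and hypotension. State the cut-offs in the SAP.

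The cost is one derivation and one table from data already collected, with no change to study conduct. If the sponsor intends grading to be reported only through the AE and reactogenicity tables, one sentence in 5.3.3.11 should say so. That would settle how 8.3.6 is to be read, but post-dose falls would still be hidden unless the minimum reading is summarised alongside the maximum.

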8.3.7. Electrocardiogram

A 12-lead electrocardiogram (ECG) will be performed at Screening, the end of the Treatment Period (Day 169 or ET), and at the end of the Follow-up Period (Day 505 or ET), as indicated in the Schedule of Events (Section 4.6). At visits with laboratory assessments, ECGs should be measured before any blood sample collection. Any clinically relevant change in physical examination findings will be recorded as AEs. Any clinically relevant change in ECG findings will be recorded as AEs.

9. ADVERSE EVENTS

9.1. **Definitions**

9.1.1. Adverse Event

An AE is defined as any untoward medical occurrence associated with the use of a drug in humans, whether or not considered drug related. An AE can therefore be any unfavorable and unintended sign (including an abnormal laboratory finding), symptom, or disease temporally associated with the use of the investigational product whether or not related to the investigational product. An AE can be any sign, symptom, or diagnosis that appears or changes in intensity during the course of the study.

Unchanged chronic conditions are not AEs and should not be recorded on the AE pages of the eCRF. These medical conditions should be adequately documented on the appropriate page of the eCRF (medical history or physical examination). However, medical conditions present on the first day of treatment that worsen in intensity or frequency during the treatment or post-treatment periods in a manner not consistent with natural disease progression should be reported and recorded as AEs. The Investigator will actively solicit this information and assess the event in terms of severity and relationship to the study treatment regimen.

The term AE is used to include any AE whether serious or not serious.

9.1.2. Adverse Drug Reaction

All noxious and unintended responses to a medicinal product related to any dose should be considered an adverse drug reaction. A reaction means that a causal relationship between a medicinal product and an AE is at least a reasonable possibility, i.e., the relationship cannot be ruled out.

9.1.3. Unexpected Adverse Drug Reaction

An unexpected adverse drug reaction is defined as an adverse reaction, the nature or severity of which is not consistent with the reference safety information in the Investigator's Brochure.

For the purpose of expedited reporting of unexpected serious adverse drug reactions (ie, Suspected Unexpected Serious Adverse Reactions [SUSARs]), only possibly or probably related and unexpected SAEs (Section 9.3.2) will be considered serious adverse drug reactions.

9.1.4. Medically Attended Adverse Event

An MAE is an AE resulting in hospitalization, emergency room visit, or visit to or from medical personnel (other than routine health care visits).

